8.4.5 Medication error

If a medication error occurs in the course of the study, then the Investigator or other site personnel informs the appropriate AstraZeneca representatives within 1 day i.e., immediately but no later than 24 hours of when he or she becomes aware of it.

The designated AstraZeneca representative works with the Investigator to ensure that all relevant information is completed within 1 (Initial Fatal/Life-Threatening or follow up Fatal/Life-Threatening) or 5 (other serious initial and follow up) calendar days if there is an SAE associated with the medication error (see Section 8.3.2) and within 30 days for all other medication errors.

The definition of a Medication Error can be found in Appendix B.

8.5 Pharmacokinetics

Blood samples for determination of MEDI0382 in plasma will be taken at the times presented in the Study Plan (Table 2).

Drug concentration information that would unblind the study will not be reported to investigative sites or blinded personnel until the study has been unblinded.

8.5.1 Determination of drug concentration

Samples for determination of drug concentration will be analysed by a selected laboratory on behalf of AstraZeneca, using an appropriate bioanalytical method. Full details of the analytical method used will be described in a separate bioanalytical report.

8.5.2 Storage and destruction of pharmacokinetic samples

PK samples will be disposed of after the Bioanalytical Report finalization or six months after issuance of the draft Bioanalytical Report (whichever is earlier), unless requested for future analyses.

Pharmacokinetic samples may be disposed of or destroyed and anonymised by pooling. Additional analyses may be conducted on the anonymised, pooled pharmacokinetic samples to further evaluate and validate the analytical method. Any results from such analyses may be reported separately from the CSR.

8.6 Immunogenicity

Instructions for MEDI0382 immunogenicity (ADA) sample collection, processing, storage, and shipment can be found in the Laboratory Manual. Serum samples for analysis of ADA will be collected for subjects on MEDI0382/Placebo arms according to the schedule presented in the Study Plan (Table 2). A screening assay will be used to determine ADA-positive samples. This will be in the form of a traditional ligand-binding “bridging” assay using electrochemiluminescence. Any positive samples will be tested in a confirmatory assay whereby the specificity of the ADA response will be confirmed as either positive or negative with respect to MEDI0382. Cross-reactivity of ADA-positive samples to GLP-1 and glucagon may also be assessed in the confirmatory assay. Titre evaluation will be performed on samples that are confirmed positive for ADA. For subjects with a confirmed positive ADA result, a qualitative analysis of incretin hormone levels in response to MMT (i.e., glucagon, GLP-1, glucose, and insulin) will also be performed to assess whether any correlation exists between the response and ADA positivity.

At the end of study visit, if a subject’s sample is confirmed ADA positive, the subject will be asked to return to provide another sample in as close as 3 months at the end of study visit to evaluate whether or not ADA positivity is persist. If the sample taken in 3 months is ADA positive, the subject will be asked to return to provide a sample in another 3 months (Approximately 6 months after the end of study visit). If the sample is ADA positive at 6 months, the investigator and the study physician will discuss what further action will be taken. The results of ADA in 3 months and 6 months at the end of study will not be recorded in the CRF module and the database. Serum samples collected for ADA should be stored for 2 years after marketing approval, and they may be utilised for further characterisation of the antibody response.

8.7 Pharmacodynamics

Mixed-meal Test

Following a minimum 8-hour overnight fast and at 2.5 hours after administration of IP, the subject will undergo a MMT. For the MMT, the subject will consume a standardised meal (ENSURE H, a nutritional supplement containing the components of fat, carbohydrate and protein, which make up a standard MMT) within 5 minutes, and timed serial blood samples will be obtained for measurement of glucose and parameters related to glucose metabolism through 240 minutes after consumption of the standardised meal (with no additional food intake during this time). The MMT procedures will be performed at the time points specified in the schedules. The time points are also summarized in SoA.

The timed pre- and post-MMT blood sample collections are for measurement of a panel of glucose metabolism markers: glucose, insulin, pro-insulin, c-peptide, GLP-1 and glucagon, as indicated in the example schedule for PK and PD/efficacy in Table 3 and Table 4. Glucose measurements from these pre- and post-MMT samples will be used for the primary efficacy assessment. All MMT test results will be used to generate PD profiles.

8.7.1 Collection of samples

Blood will be drawn 15 minutes before consuming the standardised meal, and at 15, 30, 45, 60, 90, 120, 180, and 240 minutes (± 5 minutes) after consumption. Blood sampling should occur as close as possible to the specified times for the MMT. Sampling ± 5 minutes of the specified time will not be considered a protocol deviation but the exact time of sampling should be recorded.

8.7.2 Storage, re-use and destruction of pharmacodynamic samples

The primary PD samples will be stored for a maximum of 15 years from the date of the Last Subject's Last Visit, after which they will be destroyed. The results of any investigation will be reported either in the CSR itself or as an addendum, or separately in a scientific report or publication.

8.8 Genetics

Participation is optional. Subjects who do not wish to participate in the genetic research may still participate in the study.

See Appendix D for Information regarding genetic research. Details on processes for collection and shipment and destruction of these samples can be found in Appendix D.

8.9 Biomarkers

Biomarkers are not evaluated in this study.

9 STATISTICAL CONSIDERATIONS

9.1 Statistical hypotheses

One of the primary objectives of this study is to assess the safety of MEDI 0382 100 µg, 200 µg, or 300 µg up-titration regimen compared with Placebo, as measured by the incidence of AEs (including SAEs), 24-hour heart rate and ABPM, safety laboratory measurements and digital ECGs. For the safety objective, no formal hypothesis testing will be carried out. Safety evaluation will be done in a descriptive manner.

The other primary objective is to explore the efficacy of MEDI0382 100 µg, 200 µg or 300 µg up-titration regimen compared with placebo, as measured by percent change from baseline to Day 48 in MMT glucose $AUC_{(0-4h)}$ and body weight. For efficacy objective, pair-wise comparison of each MEDI0382 dose vs. Placebo will be made in an exploratory manner, each at significance level of 0.05, without multiplicity adjustment.

9.2 Sample size determination

Approximately 60 patients are to be randomized to Placebo, MEDI0382 100 µg, 200 µg, and 300 µg in a ratio 1:1:1:1.

Assuming approximately 10% drop out during study, approximately 13 subjects are expected to be evaluable per treatment groups.

Assuming standard deviation of percent change in MMT glucose $AUC_{(0-4h)}$ of 20%, approximately 13 patients per arm would provide more than 80% power to detect 23% difference in percent change of MMT glucose $AUC_{(0-4h)}$ for pair - wise comparison between each of MEDI0382 dose group and Placebo each at two-sided $\alpha = 0.05$, without formal multiplicity adjustment.

Assuming standard deviation of percent change from baseline in body weight of 2.5%, the same number of subjects would provide approximately 68% power to detect mean difference of 2.5% at two-sided $\alpha = 0.05$ without formal multiplicity adjustment.

9.3 Populations for analyses

For purposes of analysis, the following populations are defined:

Population	Description
Enrolled	All subjects who signed the ICF
Randomised Set	All subjects who received randomisation number.
Full Analysis Set	All randomised subjects who received at least one dose of IP. Subjects will be analysed according to randomized treatment.
Safety analysis set	All randomised subjects who take at least 1 dose of IP. Subjects will be analysed according to treatment they received.
PK analysis set	The PK population includes all subjects who received at least one dose of MEDI0382 and had at least one post-baseline MEDI0382 PK sample taken that is above the lower limit of quantitation.

9.4 Statistical analyses

All personnel involved with the analysis of the study will remain blinded until database lock and Clinical Study Protocol deviations identified.

Analyses will be performed by AstraZeneca or its representatives. A comprehensive statistical analysis plan (SAP) will be developed and finalised before database lock and will describe the subject populations to be included in the analyses, and procedures for accounting for missing, unused, and spurious data. This section is a summary of the planned statistical analyses of the primary and secondary endpoints. Any deviations from this plan will be reported in the clinical study report.

9.4.1 Efficacy analyses

Efficacy analyses will be carried out for FAS.

Percent change from baseline in MMT Glucose $AUC_{(0-4h)}$ to Day 48 will be analysed with ANCOVA model with treatment group as a factor and baseline as a covariate. Least squares mean (LSMean)s and their 95%CIs for percent changes from baseline for each treatment group, as well as difference in LSMeans, 95%CI and nominal p-values will be provided for pair-wise comparison of each MEDI0382 dose vs. Placebo group. For subjects who prematurely discontinued study drug, the last on-treatment measurement regardless of rescue will be used for this analysis. Percent change from baseline to Day 48 in body weight will be analysed similarly.

Secondary efficacy variables will be analysed by ANCOVA or other appropriate models. Details will be provided in Statistical Analysis Plan.

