- i. MMT Schedule: Following a minimum 8-hour fast, blood samples for the tests indicated will be taken 15 minutes before the subject drinking 1 entire can of Ensure H as a standardised meal. On Day -1, and Day 48, after consumption of the standardised meal, blood samples will additionally be taken at 15, 30, 45, 60, 90, 120, 180, and 240 minutes (\pm 5 min) for glucose and insulin; 15, 45, 90, 180, and 240 minutes (\pm 5 min) for pro-insulin, c-peptide, GLP-1 and glucagon. If subject discontinues the investigational product, MMT should not be performed at the withdrawal visit.
- j. CGM device to be fitted and worn continuously during the measurement period. The sensor should be applied to the arm, taking into account which side the subject sleeps on and also which side the ABPM device will be applied to. The sensor applied to the skin is for single use and may not be reattached once removed.
- k. CGM sensors should be changed at each interval at the same time of day (\pm 20 minutes). For example, if the sensor is applied at 6:00 am on Day 1, it should also be applied at 6:00 am (\pm 20 minutes) predose on Day 6, Day 13 and Day 41. If the sensor fails, or needs to be replaced, it should be reapplied as soon as possible. The sensor can be replaced on Day 34 if the subject cannot visit on Day 41.
- l. ADA Sampling Schedule: Day 1 (V3) predose; Day 13 (V9) predose; Day 20 (V10) predose; Day 48 (V12) predose; and 7 to 14 days after administration of the last dose in the study.
- m. SAEs collected after informed consent signed and AEs after randomization will be assessed.
- n. Injection Site Assessment Schedule: The injection site will be assessed by site staff at 4 hours postdose on Day 1 and the first day of each new dose level, and at 24 hours (prior to next dose) postdose on Day 1. The site staff will not be required to assess injection sites except for the above time points. Subjects will be instructed to contact the site if there is any abnormality observed at the injection site.
- o. For withdrawal subjects, assessment should be done after decision of the withdrawal.

Table 3 Example Schedule for Mixed Meal Test (MMT) on Day -1

Example Clock Time	MMT Blood sampling (time window \pm 5 minutes)
(minimum 8-hour fast)	
9:15	15 minutes before Test Meal
9:30 ^a	Ensure H (Ensure H to be consumed within 5 minutes, actual start time to be recorded in eCRF)
9:45	15 minutes
10:00	30 minutes
10:15	45 minutes
10:30	60 minutes
11:00	90 minutes
11:30	120 minutes

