7.1.1 Procedures for discontinuation of study treatment

The investigator should instruct the subject to contact the site before or at the time of discontinuation of investigational product. If the investigational product is permanently discontinued as judged by the Investigator, the subject will be followed for protocol-specified assessments at Visit 12/Withdrawal except for MMT as well as Visit 13. Any AEs that are not resolved at the subject's last AE assessment in the study are followed up as instructed in the Section 8.3.3. The date of last intake of Study treatment should be documented in the eCRF. All investigational product should be returned by the subject at their next on-site study

visit (e.g., Visit 13). Subjects permanently discontinuing Study treatment should be given locally available standard of care therapy, at the discretion of the Investigator.

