7.3 Withdrawal from the study

A subject may withdraw from the study (e.g., withdraw consent), at any time at his/her own request, without prejudice to further treatment. A subject who discontinues study medication should be encouraged to continue in the study.

If the subject withdraws consent for disclosure of future information, the sponsor may retain and continue to use any data collected before such a withdrawal of consent.

If a subject withdraws from the study, he/she may request destruction of any samples taken, and the investigator must document this in the site study records.

A subject who withdraws consent will always be asked about the reason(s) and the presence of any adverse events (AE). The Investigator will follow up subjects as medically indicated.

See SoA, Table 2, for data to be collected at the time of study discontinuation and follow-up and for any further evaluations that need to be completed. All investigational product should be returned by the subject.

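### The last-on-treatment rule for the primary MMT glucose AUC has no value to use for any early discontinuer, so the analysis labelled FAS is in effect a completer analysis

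*Protocol*

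**What the plan says.** Section 9.4.1 of the protocol states "Efficacy analyses will be carried out for FAS". Section 9.3 defines that set as "All randomised subjects who received at least one dose of IP", analysed as randomised; no post-baseline MMT is required for membership. The percent change in MMT glucose AUC(0-4h) to Day 48 is analysed by ANCOVA with treatment and baseline. For those who stop early, 9.4.1 says: "For subjects who prematurely discontinued study drug, the last on-treatment measurement regardless of rescue will be used for this analysis". It then adds: "Percent change from baseline to Day 48 in body weight will be analysed similarly".

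The timing of the MMT is fixed in footnote i to Table 2 (section 1.1): "On Day -1, and Day 48, after consumption of the standardised meal, blood samples will additionally be taken". The same footnote says: "If subject discontinues the investigational product, MMT should not be performed at the withdrawal visit". Section 7.1.1 repeats the exclusion for permanent discontinuation: "the subject will be followed for protocol-specified assessments at Visit 12/Withdrawal except for MMT as well as Visit 13". Section 8.7 ties the MMT to dosing, placing it 2.5 hours after the investigational product is given.

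**The concern.** A carry-forward rule needs a post-baseline, on-treatment value to carry. With one MMT before the first dose, one on the last treatment day and none after stopping, no such value can exist for a subject who stops before Day 48. The rule fails for exactly the subjects it was written for, and the protocol then describes as an FAS analysis something that leaves some FAS members without a value.

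The stake is selection. Section 2.3 names nausea and vomiting as the identified risks. Appendix G, Table 10 shows nausea or vomiting in 7 of 26 subjects on MEDI0382 and 0 of 13 on placebo in Cohort 1 of Study D5670C00011. Section 2.2 reports six subjects in Study D5670C00002 with a treatment-emergent event leading to withdrawal. None of this gives a discontinuation rate by arm for the present trial, but discontinuation related to treatment or dose is plausible. Arms are small (15 each), and 6.3 says withdrawn subjects are not replaced.

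**Working it through.** **1. What each kind of subject contributes**

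| Subject | MMT Day -1 | MMT on treatment after baseline | Does the 9.4.1 rule supply a value? |
|---|---|---|---|
| On drug to Day 48 | yes | Day 48 | not needed |
| Rescued, still on drug at Day 48 | yes | Day 48 | yes: the observed value counts regardless of rescue |
| Stops drug before Day 48 | yes | none | no |

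A Day 48 MMT done off drug would not help under the rule as worded, because it would not be an on-treatment measurement. In any case 7.1.1 excludes it.

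Body weight differs. Table 2 schedules it on Days 1, 6, 13, 20, 34 and 48, so the same rule generally has a value to use.

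**2. The protocol's own power figure**

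Inputs from 9.2: 15 randomised per arm (60 in a 1:1:1:1 ratio), about 10% dropout, about 13 evaluable per arm, difference 23, SD 20, two-sided alpha 0.05.

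- Expected evaluable: 15 × 0.90 = 13.5, in line with about 13. Expected discontinuers: 15 × 0.10 = 1.5 per arm.
- Noncentrality: 23 / (20 × √(2/13)) = 2.93, with 24 degrees of freedom. Noncentral t power is 80.3%, which reproduces the stated figure of more than 80%.
- With real data on all 15 per arm, the same formula gives 86.0%.

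The sample size was therefore computed for completers, while 9.4.1 describes the analysis as FAS.

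**3. How far the completer and all-FAS answers can differ**

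Assumption: discontinuers keep no drug effect, so those on active drug have the placebo mean. With a fraction d stopping on active drug, the all-FAS difference is 23 × (1 − d).

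- d = 10%: 23 × 0.90 = 20.7. The completer value of 23 is higher by 2.3 points (2.3/20.7 = 11%).
- d = 20% (assumed; not in the protocol): 23 × 0.80 = 18.4. The completer value is higher by 4.6 points (4.6/18.4 = 25%).

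**4. What an all-FAS analysis would deliver**

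This was simulated: 15 per arm, SD 20, placebo mean about −10, active mean about −33, and missing Day 48 values multiply imputed from placebo completers given baseline and combined by Rubin's rules. The placebo mean is an assumption, suggested by the placebo result of Study D5670C00002 in section 2.2.

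| Dropout | Placebo-based imputation | Completers |
|---|---|---|
| 10% in every arm | about 21 points, power about 71 to 72% | about 23 points, about 83 to 84% |
| 20% active, 7% placebo (assumed) | about 19 points, power about 53 to 56% | about 23 points, about 80 to 82% |

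The ranges are the spread between independent simulation runs.

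**The case against.** The best defence is that 9.4 calls its text a summary and leaves procedures for missing data to a SAP finalised before database lock. The sample size already allows for non-evaluable subjects, so a completer analysis may be what was meant. The second half is persuasive, and it supports reading the text as a completer analysis. The first half does not rescue the sentence. 9.4.1 is not silent: it fixes a rule that the schedule defeats, so any workable SAP method must replace it.

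Proportion is also a fair point. Section 9.1 calls the efficacy comparisons exploratory and unadjusted, 9.4.1 gives nominal p-values, and the planned dropout affects only one or two subjects per arm. That stands, and it lowers the severity.

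Three stronger readings are tempting and are not supported:

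- A reader might infer that the primary analysis cannot be run at all. It can. The ANCOVA is well defined for everyone with a Day 48 MMT; only the sentence on discontinuers is empty, and only for this endpoint.
- A reader might infer that baseline is to be carried forward as 0% change. At 10% dropout in every arm, that would give 20.7 points and 77 to 80% power for a placebo change between −10% and 0%. But the Day -1 value precedes the first dose and is not on treatment, so the wording does not lead there.
- A reader might see a contradiction between 7.1.1 and the request in 7.3 that "A subject who discontinues study medication should be encouraged to continue in the study". Encouragement to stay and a reduced set of assessments can coexist.

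**Conclusion.** The concern holds for the MMT glucose AUC(0-4h) endpoint only. The last-on-treatment rule in 9.4.1 has nothing to act on. Followed as written, it turns an analysis described as FAS into one of subjects with an observed Day 48 MMT. The stated power is arithmetically correct, but it belongs to that completer analysis.

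The size is modest at the planned dropout: about 2.3 points of 23 if discontinuers keep no drug effect. It grows if active-arm subjects stop more often. The 20% versus 7% rates, the placebo mean and the loss of effect after stopping are assumptions, not protocol figures. If discontinuation is unrelated to outcome, completers are not biased and the fault is one of labelling.

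Severity: should be fixed, not must be fixed, given the exploratory status of the comparisons.

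**What to change.** In 9.4.1, restrict the last-on-treatment rule to body weight. For the MMT, state that the main ANCOVA uses subjects with an observed Day 48 MMT and label it so, not as an FAS analysis. Prespecify, before unblinding, at least one sensitivity analysis that keeps all FAS subjects. Placebo-based multiple imputation given baseline AUC is one option; it targets a different quantity from the on-treatment one that 9.4.1 aims at, which is a reason to use it as a sensitivity analysis. Make 9.4.1 consistent with footnote i to Table 2, 7.1.1 and 8.7, so that the data the analysis relies on are data the schedule collects.

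The cost is protocol and SAP wording and modest programming. The sponsor should also accept openly that the all-FAS analysis gives a smaller estimate and less power: about 21 points and 72% at 10% dropout in every arm, and about 19 points and 56% at the assumed 20% versus 7%, under the assumptions above. No change to sample size, visits or the main ANCOVA model is needed.

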9.4.2 Safety analyses

Safety analysis will be based on Safety set.

Adverse events will be coded using the Medical Dictionary for Regulatory Activities (MedDRA). The type, incidence, severity and relationship to investigational product of each AE will be summarized by MedDRA System Organ Class and Preferred Term, using number and percentage of patients with certain events. AEs with onset on or after first day of IP will be mainly evaluated. Other safety variables such as 24-hour ABPM, vital signs, ECG and safety laboratory tests will be summarized descriptively by treatment and visit, as appropriate.

9.4.3 Other analyses (PK)

Individual MEDI0382 plasma concentrations will be summarised by treatment and visit. MEDI0382 plasma concentration at trough (C_{trough}) may be summarised by treatment and visit using descriptive statistics for the MEDI0382 treatment arms.

A population PK analysis may be performed to further evaluate the PK properties of MEDI0382, but will not be reported in the CSR.

The immunogenicity of MEDI0382 will be evaluated. The number and percentage of subjects with confirmed positive serum antibodies to MEDI0382 will be reported by dose level. Data on titres and cross-reactivity to GLP-1 and glucagon (where applicable) will be listed. If warranted by the data, the association of ADA positive with observed PK data may be explored.

Pharmacodynamic, and biomarker exploratory analyses will be described in the SAP finalised before database lock. The pharmacodynamic analyses will be presented separately from the main CSR.

